**LIST OF ABBREVIATIONS AND RELEVANT DEFINITIONS**

ABR	General Assessment and Registration form (ABR form), the application form that is required for submission to the accredited Ethics Committee; in Dutch: Algemeen Beoordelings- en Registratieformulier (ABR-formulier)
AE	Adverse Event
AR	Adverse Reaction
CA	Competent Authority
CCMO	Central Committee on Research Involving Human Subjects; in Dutch: Centrale Commissie Mensgebonden Onderzoek
CV	Curriculum Vitae
DFU	Diabetic Foot Ulcer
DSMB	Data Safety Monitoring Board
EU	European Union
EudraCT	European drug regulatory affairs Clinical Trials
GCP	Good Clinical Practice
GDPR	General Data Protection Regulation; in Dutch: Algemene Verordening Gegevensbescherming (AVG)
HBOT	Hyperbaric Oxygen Therapy
IB	Investigator's Brochure
IC	Informed Consent
METC	Medical research ethics committee (MREC); in Dutch: medisch-ethische toetsingscommissie (METC)
MAMS	Multi-arm, multi-stage study design
PAOD	Peripheral arterial occlusive disease
(S)AE	(Serious) Adverse Event
SmPC	Summary of Product Characteristics; in Dutch: officiële productinformatie IB1-tekst
Sponsor	The sponsor is the party that commissions the organisation or performance of the research.
SUSAR	Suspected Unexpected Serious Adverse Reaction
UAVG	Dutch Act on Implementation of the General Data Protection Regulation; in Dutch: Uitvoeringswet AVG
WMO	Medical Research Involving Human Subjects Act; in Dutch: Wet Medisch-wetenschappelijk Onderzoek met Mensen

**SUMMARY**

**Rationale:** Diabetes is a major healthcare problem with a high incidence and morbidity. Diabetic foot ulcers (DFUs) are a major complication of diabetes, often associated with peripheral arterial occlusive disease. Currently available evidence shows HyperBaric Oxygen Therapy (HBOT) can reduce major amputation rate, but clinicians remain sceptical about the (cost-) effectiveness and feasibility of HBOT for ischemic DFUs in clinical practice. Therefore, international vascular surgeons and HBOT-physicians feel a strong need for a sufficiently powered clinical trial to determine whether and how many HBOT-sessions may be a (cost-) effective adjunctive treatment to ischemic DFUs.

**Objective:** The primary objective is to assess the (cost-) effectiveness of HBOT in addition to standard wound care and vascular surgical treatment for patients with a DFU and leg ischemia.

**Study design:** An international, multi-arm multi-stage (MAMS) design is chosen to conduct an efficient randomised clinical trial. At a planned interim analysis the best performing study arm(s) will be chosen to continue.

**Study population:** We need up to 544 patients with a Meggitt-Wagner stage 3 or 4 DFU and proven peripheral ischaemia.

**Intervention:** Patients will be randomised to receive standard care (wound treatment and surgical interventions following international guidelines) with either 0, 20, 30 or 40 sessions of HBOT. These sessions will comprise 90-120 minutes of HBOT at a pressure of 2.2-2.5 ATA according to international standards.

**Main study parameters/endpoints:** Primary endpoints are amputation rates and amputation-free survival after 12 months. Secondary objectives are wound healing, health-related quality of life and cost-effectiveness of the interventions.

**Nature and extent of the burden and risks associated with participation, benefit and group relatedness:** All patients will receive standard wound care and (if possible) endovascular or surgical revascularization, irrespective of their allocation. HBOT is a generally accepted and reimbursed indication for the treatment of DFUs. The risks of HBOT are regarded as low. Patients in the HBOT groups will undergo 20, 30 or 40 HBOT sessions. Patients will be asked to fill in questionnaires at four time points, and to score their pain weekly during the first 8 weeks. Three visits to their outpatient surgical clinic will be scheduled, which do not deviate from usual care.

## 1. INTRODUCTION AND RATIONALE

Diabetes is a major healthcare problem with an estimated incidence of 422 million people worldwide (WHO 2019) and 1.2 million in the Netherlands (Diabetesfonds 2019). Besides blindness, kidney failure, heart attacks and strokes, a major burden of diabetes is the occurrence of diabetic foot ulcers (DFUs). Diabetes is also often associated with peripheral arterial occlusive disease (PAOD). Despite optimal treatment, DFUs are the main cause of lower extremity amputations, especially in the presence of leg ischemia. Two out of three amputations are diabetes-related, with a yearly amputation rate of 2.5% for diabetic patients (Lombardo et al., 2014).

The treatment of diabetic foot ulcers (DFU) is an approved indication for hyperbaric oxygen therapy (HBOT), as acknowledged by the European, American and South-Pacific hyperbaric societies (EUBS, UHMS and SPUMS; Weaver 2014). Therefore, HBOT is reimbursed for this indication in many countries, including the Netherlands. The evidence for this effectiveness has been based on systematic reviews of (relatively few and small) clinical trials that included both ischemic and non-ischemic DFUs (O'Reilly 2013, Stoekenbroek 2014, Kranke 2015). Later systematic reviews, including more recent evidence, showed that HBOT appears effective for ischemic DFUs (Brouwer 2020), rather than for non-ischemic DFUs (Lalieu 2019). Hence, ischemia should be discerned when considering HBOT for DFUs (Brouwer 2020).

The largest and most recent DAMOCLES trial on HBOT for ischemic DFUs (Santema 2018a) showed some promising results for HBOT as an adjunctive treatment for patients with ischemic DFUs. However, the treatment effect was not convincing, due to the limited number of patients available for inclusion in a single country, as well as the inclusion of relatively superficial, uninfected (Meggitt-Wagner class 2) DFUs (Santema 2018b). They found 10% fewer major amputations after 12 months in patients treated with HBOT in their intention-to-treat analysis, but this was not statistically significant. In the per-protocol analysis a significant reduction of major amputations (17%) observed. Amputation-free survival (AFS) after HBOT was 13% higher in the intention-to-treat analysis, which was not statistically significant. In the per-protocol analysis the AFS was significantly (26%) higher as opposed to standard treatment. No significant effect was found on complete ulcer healing in neither the intention-to-treat nor the per-protocol analysis.

The recent meta-analysis (Brouwer 2020) of currently available evidence shows that HBOT may lead to a 15% reduction of major amputation rate, but shows no effect on minor amputation, CUH, or mortality. To date, substantial scepticism still exists among clinicians due to the limited and conflicting evidence for its (cost-)effectiveness to promote wound healing and prevention amputations or amputation-free survival. Hence, a strong need is felt internationally among vascular surgeons and HT-physicians for a sufficiently powered clinical trial that is able to determine whether HBOT is a (cost-)effective treatment for ischemic DFUs.

## 2. OBJECTIVES

The aim of the study is to confirm or refute the hypothesis that HBOT is (cost-) effective as an adjunctive treatment to standard wound care for patients with an ischemic DFU to prevent major amputations and to establish the optimal number of sessions to obtain this purported effect.

Primary Objective:

Amputation rate and amputation-free survival

Secondary Objective(s):

- Cost-effectiveness and budget impact
- Complete wound healing
- Health-related quality of life
- Pain scores
- Need for additional (vascular) interventions
- TcpO2 before, during and after HBOT

### 3. STUDY DESIGN

Multinational randomized clinical trial with an adaptive (multi-arm, multi-stage; MAMS) design, with a follow-up of 12 months, following the (extended) CONSORT-statement. We will have four study arms and two stages (one interim and one final analysis; see figure 1 below). Patients will be randomized to receive standard treatment with 0, 20, 30 or 40 HBOT treatments.

The more efficient MAMS design (Sydes 2018, Sydes 2012, Wason 2012) for clinical trials includes a planned interim analysis, based on which only the best performing study arms will be chosen to continue. This will reduce the total number of patients required and the number of patients receiving an ineffective treatment, because after the interim analysis no patients will be included in less effective treatment arms.

[figure not shown]

Figure 1 Flow of patient inclusion and analysis

## **4. STUDY POPULATION**

### **4.1 Population (base)**

Consecutive patients with type I or II diabetes, a DFU and leg ischemia, presenting at the vascular surgery departments of the participating hospital. Also, HBOT centers and general practitioners may refer patients to the vascular surgery departments for inclusion in the study. Both patients suitable and unsuitable for vascular repair are eligible for inclusion.

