### **4.2 Inclusion criteria**

In order to be eligible to participate in this study, a subject must meet all of the following criteria:

1. Type I or II diabetes
2. Meggitt-Wagner 3 or 4 lower extremity ulcer(s), present for at least 4 weeks or after a minor amputation because of a previously existing ischemic DFU on a toe or forefoot. In case more than one ulcer is present, the largest will be observed as target ulcer
3. Leg ischemia, characterized by a highest ankle systolic blood pressure < 70 mmHg, **or** a toe systolic pressure < 50 mmHg **or** a TcpO2 < 40 mmHg
4. Complete assessment of peripheral arterial lesions from the aorta to the pedal arteries with duplex ultrasonography, magnetic resonance angiography, computed tomography angiography and/or intraarterial digital subtraction angiography of the ipsilateral leg
5. Adults
6. Written informed consent

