### **4.3 Exclusion criteria**

A potential subject who meets any of the following criteria will be excluded from participation in this study:

1. Chronic Obstructive Pulmonary Disease (COPD) GOLD IV
2. Treatment with chemotherapy, immunosuppressive drugs or systemic corticosteroids within last 3 months, as this interferes with normal wound healing
3. End-stage renal disease requiring dialysis
4. Metastasized malignancy
5. Left ventricular failure with ejection fraction (EF) <20% or external pacemaker
6. Pregnancy
7. Insufficient proficiency of local language/English, or inability to complete the questionnaires

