**5.2 Use of co-intervention (if applicable)**

HBOT will be given in addition to standard care according to local best practice in expertise centers and will not intervene with the usual care. Although (vascular) interventions are preferably performed before the start of HBOT, participation in the study will not influence any additional interventions that might be needed during follow-up ((endo)vascular interventions, amputations, wound debridement, medication, etc).

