#### 7.6 Follow-up of subjects withdrawn from treatment

Patients who withdraw from the study for any reason will not be followed conform ethical and legal protocols. They may continue their regular treatment (including HBOT if desired) follow-up moments.

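### The protocol admits patients already given HBOT for the target ulcer and schedules no count of sessions received, which can blur the 0/20/30/40-session comparison

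*Protocol*

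**What the plan says.** The randomised factor is the number of HBOT sessions: 0, 20, 30 or 40 on top of standard care (Protocol section 3). Section 2 makes the optimal number of sessions part of the aim.

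**Who can enter**
- Section 4.1 names HBOT centres as a source of patients: "Also, HBOT centers and general practitioners may refer patients to the vascular surgery departments for inclusion in the study".
- Section 1 states that "HBOT is reimbursed for this indication in many countries, including the Netherlands".
- Section 4.2 requires an ulcer "present for at least 4 weeks or after a minor amputation because of a previously existing ischemic DFU on a toe or forefoot".
- Section 4.3 lists seven exclusions. One covers earlier treatment: "Treatment with chemotherapy, immunosuppressive drugs or systemic corticosteroids within last 3 months, as this interferes with normal wound healing". None mentions HBOT.
- Section 7.2 stratifies by centre and by entry with a minor amputation, not by earlier HBOT.

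**HBOT after randomisation**
- Section 5.2 says that "participation in the study will not influence any additional interventions that might be needed during follow-up". Its list of examples does not name HBOT and ends open.
- Section 7.6 says of withdrawn patients: "They may continue their regular treatment (including HBOT if desired) follow-up moments". The same section says that these patients are not followed.

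**What is recorded**
- Table 1 (section 7.3) has no row for HBOT sessions before entry, under allocation or outside it.
- HBOT use appears only within the economic data: volumes and costs in section 7.1, and costs during follow-up in section 7.1.2.

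**The concern.** When the tested factor is a count of sessions, each arm's label should describe the exposure it stands for. Here a patient can have begun HBOT for the target ulcer, be referred by the centre that gave it, and be randomised to 0 or to 20 further sessions. The criteria as written admit that patient, and no scheduled assessment captures the earlier sessions.

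Two things are at stake. First, such patients can narrow the difference between arms, because part of the exposure under test was given before randomisation in every arm. Second, the session-number question loses its meaning for them: an allocation of 20 is then 20 plus an unknown number. HBOT obtained outside the allocation after randomisation would have a similar effect and would also go uncounted, apart from what the cost data pick up. If the trial then found little difference between arms, nobody could say how far mixed exposure had contributed.

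**Working it through.** **1. Is earlier HBOT realistic under the entry criteria?** Section 4.2 asks for an ulcer of at least 4 weeks (or a minor amputation). Section 5.1 prefers 5 sessions per week. 4 weeks × 5 sessions = 20 sessions, as many as the smallest active arm. So there is time before entry for a substantial course. How often this happens is not documented.

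**2. Does the sample size allow for it?** Section 4.4 gives 68 patients per group per stage.
- 68 × 4 arms × 2 stages = 544, as stated.
- 544 / 0.95 = 572.6, rounded up to 573, as stated.

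Both totals reproduce. The only inflation is for loss to follow-up; nothing is allowed for HBOT outside the allocation.

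**3. How much could HBOT in the control arm after randomisation cost?** Inputs from section 4.4: 26% amputations in controls, 11% with HBOT, one-sided 5%. An arm present in both stages has 2 × 68 = 136 patients. Assumption: a share c of controls obtains the full HBOT effect after randomisation. No document gives c, so a range is shown.

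- Control rate: p(c) = 0.26 − 0.15c
- Difference: p(c) − 0.11
- SE(c) = √{[p(c)(1 − p(c)) + 0.11 × 0.89] / 136}
- Power = Φ(difference / SE − 1.645)

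For c = 0: SE = √[(0.1924 + 0.0979)/136] = 0.0462; 0.15/0.0462 = 3.247; 3.247 − 1.645 = 1.602; power 94.5%.

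| c | Control rate | Difference (points) | SE | Pairwise power | n per arm for 90% |
|---|---|---|---|---|---|
| 0% | 26.0% | 15.0 | 0.0462 | 94.5% | 113 |
| 10% | 24.5% | 13.5 | 0.0456 | 90.6% | 136 |
| 20% | 23.0% | 12.0 | 0.0450 | 84.7% | 166 |
| 30% | 21.5% | 10.5 | 0.0443 | 76.6% | 210 |

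With another common variance convention the powers are 94.2%, 90.1%, 84.2% and 76.1%; the n column uses that convention. All are single comparisons without correction for three active arms, so they show the slope of the loss and are not the trial's own power.

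**4. Same assumption in a two-stage, four-arm design.** A binomial simulation used 68 per group per stage, one arm at 11% and two at 21%, and three boundary shapes (O'Brien-Fleming, Pocock, triangular) set to a 5% one-sided family-wise error. The chance of selecting the effective arm is 82–87% at c = 0, 75–80% at 10%, 66–72% at 20% and 55–61% at 30%. The protocol does not state its boundary shape, hence the ranges.

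**5. What steps 3 and 4 do not measure.** They model HBOT obtained by controls after randomisation. They do not size the effect of earlier HBOT. That depends on how many patients had it and what they would still gain from more sessions, and the documents give neither.

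**The case against.** The strongest reply is that much of this rests on silence. Referral from an HBOT centre may simply mean that a patient sent there for treatment is redirected for randomisation before starting, and no passage says otherwise. Section 5.1 ties the sessions to the randomisation and section 3 fixes one arm at 0, which implies that HBOT follows the allocation. Session volumes are partly covered by the cost data, and the patient-characteristics row of Table 1 is not itemised, so treatment history might be collected there.

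These points limit the concern but do not remove it. Eligibility is decided by section 4.3, and its list does not keep pre-treated patients out, although it excludes other recent treatments because they disturb wound healing. Cost data during follow-up cannot show sessions given before entry.

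Four stronger readings are tempting, and the documents do not support them:
- *HBOT outside the allocation is open to every arm.* It is expressly allowed only after withdrawal (section 7.6). Those patients are not followed, so the result there is missing outcomes, not observed crossover. For patients who stay, there is simply no rule.
- *Earlier HBOT biases the trial in one direction between arms.* It precedes randomisation and is balanced in expectation.
- *The previous trial shows crossover.* Section 1 reports 10 points fewer major amputations by intention to treat and then "In the per-protocol analysis a significant reduction of major amputations (17%) observed". It does not say why the figures differ. Incomplete courses in the active arm, or selection into the per-protocol set, would look the same.
- *Planning intention to treat alone is a defect.* It is not. Deviation handling and any analysis by sessions received can be left to a statistical analysis plan.

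**Conclusion.** The point holds in a limited form. In a trial whose tested factor is the number of HBOT sessions, the eligibility list admits patients already treated with HBOT for the target ulcer, and no scheduled assessment counts sessions received. Earlier HBOT can shrink the contrast between arms and makes the allocated number an unknown total. Its size cannot be estimated from the documents.

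For HBOT outside the allocation after randomisation, the illustrative loss of pairwise power is from about 94% to 91%, 85% and 77% at 10%, 20% and 30% of controls. This rests on an undocumented rate, on those controls receiving the full effect, and on an unadjusted single comparison. At 10% the pairwise loss is modest. The reason to act is that the change is cheap and that exposure not recorded at the time cannot be reliably reconstructed. The design is not invalid as it stands, but the change should be made.

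**What to change.** 1. Section 4.3: add an exclusion for patients who have already received HBOT for the current target ulcer.
2. Table 1 (section 7.3): add a row, for all arms including 0 sessions, for the number and dates of HBOT sessions received before entry (for example for another ulcer), under allocation and outside it.
3. State that patients remain in the intention-to-treat set whatever HBOT they received.

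Whether HBOT outside the allocation is permitted during follow-up is a clinical decision for the sponsor; the request here is only that it be recorded.

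Cost: a small loss of eligible patients, and one eCRF item that the cost analysis largely needs already. No change to the sample size or the primary analysis is required.

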### **4.2 Inclusion criteria**

In order to be eligible to participate in this study, a subject must meet all of the following criteria:

1. Type I or II diabetes
2. Meggitt-Wagner 3 or 4 lower extremity ulcer(s), present for at least 4 weeks or after a minor amputation because of a previously existing ischemic DFU on a toe or forefoot. In case more than one ulcer is present, the largest will be observed as target ulcer
3. Leg ischemia, characterized by a highest ankle systolic blood pressure < 70 mmHg, **or** a toe systolic pressure < 50 mmHg **or** a TcpO2 < 40 mmHg
4. Complete assessment of peripheral arterial lesions from the aorta to the pedal arteries with duplex ultrasonography, magnetic resonance angiography, computed tomography angiography and/or intraarterial digital subtraction angiography of the ipsilateral leg
5. Adults
6. Written informed consent

### **4.3 Exclusion criteria**

A potential subject who meets any of the following criteria will be excluded from participation in this study:

1. Chronic Obstructive Pulmonary Disease (COPD) GOLD IV
2. Treatment with chemotherapy, immunosuppressive drugs or systemic corticosteroids within last 3 months, as this interferes with normal wound healing
3. End-stage renal disease requiring dialysis
4. Metastasized malignancy
5. Left ventricular failure with ejection fraction (EF) <20% or external pacemaker
6. Pregnancy
7. Insufficient proficiency of local language/English, or inability to complete the questionnaires

### **4.4 Sample size calculation**

The primary outcome is the probability of amputations after 12 months. The meta-analysis showed a 15% difference (11% vs. 26%; Brouwer 2020) of amputations between patients treated with HBOT and patients treated conservatively. The sample size calculation is based on a one-sided type I error of 5% and a power of 90% to control for a type 2 error. A

generalization of the power requirements for testing multiple active treatments to one control group was used as proposed by Dunnett (Dunnett 1984).

The critical values for continuation of a treatment arm are odds ratios of 0.76 and 0.352, which are in accordance with a drop in amputations from 26% to 21% and to 11%. If the difference is <5% the HBOT treatment arm is deemed futile, while a difference of 15% or higher is deemed superior. Based on these critical values the required number of patients in each group in each stage is 68, leading to a required maximum number of 544 patients. The sample size calculation is based on a generalization of Whitehead and Jaki (Whitehead 2009, Jaki 2019). Taking into account a possible loss to follow-up of 5%, we will need a total of (up to) 573 patients.

This leads to the following stopping rules and possible scenarios after the interim analysis (using the chi-square test for differences in percentages between the groups) (see figure 2 below):

- 1) If one of the HBOT treatment groups leads to a significantly less than 5% improvement in amputation rate as compared to controls (based on the expected 26% vs 21% difference, i.e. an OR of 0.76), then this treatment group will be discontinued as it is futile.
- 2) IF a HBOT treatment group proves to decrease amputation rate significantly by >15% (26% vs 11%; OR: 0.352) as compared to controls, then superiority of a treatment arm is proven and the trial will be discontinued as it has reached its aim. If more than one HBOT-treatment arm shows this superiority, the group with the lowest number of HBOT treatments is deemed superior.
- 3) If the HBOT group(s) show(s) minor improvements in amputation rate (between 5% and 15%) over control, then these groups will continue in the second stage of the trial.

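### Section 4.4 uses its sizing effects (5 and 15 points) as interim limits and states the rule in two conflicting ways; read as observed differences, it cannot give both 5% error and 90% power

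*Protocol*

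**What the plan says.** Section 4.4 aims for a "one-sided type I error of 5% and a power of 90" per cent, with three HBOT arms against one control and two stages of 68 per arm. The effects in that calculation correspond to "a drop in amputations from 26% to 21% and to 11" per cent. The same two effects serve as decision limits: "The critical values for continuation of a treatment arm are odds ratios of 0.76 and 0.352".

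The decision rule appears in two forms:

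- **Plain difference.** "If the difference is <5% the HBOT treatment arm is deemed futile, while a difference of 15% or higher is deemed superior".
- **Numbered rules.** Rule 1 drops an arm that "leads to a significantly less than 5% improvement in amputation rate as compared to controls". Rule 2 stops the trial if an arm "proves to decrease amputation rate significantly by >15% (26% vs 11%; OR: 0.352) as compared to controls". Rule 3 drops the significance wording and continues arms with "minor improvements in amputation rate (between 5% and 15%) over control".

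The named interim test is a chi-square test (sections 4.4 and 9.1). Section 9.3 places the interim at three months of follow-up and refers back to 4.4 for the decision. Section 7.7 refers to Figure 2. Section 9.1 names the log-rank test for the final analysis. No interim error rate, boundary shape or final critical value is given.

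**The concern.** The effect a trial is sized to detect and the boundary an estimate must cross are different quantities. If the superiority boundary sits exactly at the design effect, an arm with that effect has only about an even chance of crossing. The boundary's error rate is then whatever the sample size makes it, not something the design has set.

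The wording adds a second problem. An observed difference under 5 points is a very different event from one shown to be significantly under 5 points, and a chi-square test of two percentages ordinarily tests against zero, not against 5 or 15 points. This rule decides which arms survive and whether the trial ends for superiority, so two groups applying section 4.4 in good faith could act in opposite ways on the same data.

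**Working it through.** **Inputs (section 4.4 unless noted).** Control 26%; HBOT 21% or 11%; 68 per arm per stage; one-sided 5%; power 90%; three HBOT arms and two stages (also section 3); interim at three months (section 9.3).

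**The plan's own figures.**

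- Odds ratios: (0.21/0.79)/(0.26/0.74) = 0.757 and (0.11/0.89)/(0.26/0.74) = 0.352. Both agree with the text.
- Totals: 68 × 4 × 2 = 544, and 544/0.95 = 572.6, rounded up to 573.
- The 68 can be recovered on the log-odds scale with variance 1/[q(1−q)], taking q = (0.26 + 0.11 + 0.21 + 0.21)/4 = 0.1975. O'Brien-Fleming-type upper limits of z = 2.93 and 2.07, with an interim lower limit of 0, give n = 68 and power 90.1%.
- Boundary shape and variance are assumptions. Other choices give 56 to 98; a triangular shape with q = 0.235 gives 69.

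**Reading 1, observed difference.** 0.15 × 68 = 10.2, so superiority needs at least 11 fewer amputations than control. 0.05 × 68 = 3.4, so futility means at most 3 fewer.

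**Reading 2, one-sided 5% test against the margin m = 0.15 or 0.05.** z = (d − m)/√{[p₀(1−p₀) + p₁(1−p₁)]/68}, with limits ±1.645.

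- Superiority at 26% versus 11%: the standard error is √[(0.1924 + 0.0979)/68] = 0.0653, so the observed difference must exceed 0.15 + 1.645 × 0.0653 = 0.257.
- Futility at 26% versus 21%: the standard error is √[(0.1924 + 0.1659)/68] = 0.0726, so the limit is 0.05 − 1.645 × 0.0726 = −0.069. The arm must look about 7 points worse than control.
- In counts, with 18/68 control amputations, an HBOT arm is superior only at 1/68 or fewer and futile only at 24/68 or more.

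**Simulation.** 1,000,000 binomial trials per scenario. The null has 26% in all arms; the design case has 26/11/21/21%. Dropped arms cannot win later. Power is the chance that the 11% arm is declared superior.

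| | Reading 1 | Reading 2 |
|---|---|---|
| Zero-effect arm dropped at interim | 75% | 17% |
| 11% arm superior at interim | 47% | 5% |
| Any arm superior at interim, null | 4.9% | 0.05% |
| Whole trial, final Dunnett z 2.06: error / power | 7.7–7.8% / 85% | 5.1% / 88% |
| Whole trial, final z 3.0: error / power | 5.0% / 65% | not run |

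Under reading 1, lowering the final limit to 1.645 restores power to 90% but raises error to about 12%. No final limit gives both 5% and 90%.

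**Sensitivity.** The interim uses three-month data and the protocol gives no three-month rate. If the null rate then is 20% or 15%, reading 1's interim error is 3.0% or 1.5%.

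**A third reading of rule 2:** at least 15 points and also significant against zero. At these sample sizes almost every observed difference of 15 points or more is already significant, so the superiority error is essentially that of reading 1.

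**The case against.** **Neither reading meets 5% and 90%.** A reader might infer this, but the document does not support it for reading 2. With a Dunnett-type final value, which section 4.4 points towards, reading 2 gives 5.1% and 88%. That is no worse than the O'Brien-Fleming-type design that reproduces 68 (about 5.2% and 87% on binomial data).

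**Some interim results have no rule.** A reader might also infer that an observed 3 points not significantly below 5, or 20 points not significantly above 15, is left undecided. The plain sentence covers both cases, as futile and superior. This is a conflict between statements, not a gap. Figure 2 could not be seen and may show one rule clearly.

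**The limits are close to a valid boundary.** A triangular design has interim limits of z = 2.33 and 0.78, which are about 15.4 and 5.6 points at 68 per arm. With 16 to 19 control amputations it decides exactly as reading 1 does. With the same final value (2.19), power is 83% for both and error is 6.9% for reading 1 against 5.2%. This stands: the excess error under reading 1 is real but modest.

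**The final test is not stated, and an SAP may supply it.** This also stands, so every whole-trial figure is conditional on an assumed final value. Requiring 15 points again at the end would cut power to 60%, but nothing in the protocol says so. The conflict remains, because the protocol itself fixes the interim rule and fixes it in two ways.

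**Conclusion.** The point holds in this form. Section 4.4 uses its sizing effects as interim limits and states the decision rule in two ways that cannot both be followed. The conflict does not depend on any assumed rate, and its consequence is large: 75% versus 17% for dropping a useless arm, and 47% versus 5% for stopping on the design effect.

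Read as observed differences, the rule cannot give both 5% error and 90% power at the protocol's own rates. This rests on a 26% null rate at the interim. The excess shrinks at lower rates: with 15% at both looks and a final value of 2.06, whole-trial error is 5.1%.

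Read as significance tests against 5 and 15 points, the fault is not error control or a large loss of power. The interim hardly ever stops an arm or the trial. That defeats the purpose given in section 3, to continue only the best-performing arms, and what section 9.3 calls the main feature of the design.

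**What to change.** In section 4.4, state that odds ratios 0.352 and 0.76 are the effects used for sizing. Reconcile the plain sentence and rules 1 to 3 into one rule, given as the interim upper and lower Z boundaries and the matching final critical value of the calculation that produced 68 per arm (three active arms, two stages, one-sided 5%). Delete the percentage-point limits and the *significantly* wording, and check Figure 2 against the result.

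The boundary shape is not stated, so these are illustrations only, with 68 per arm and binomial data:

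- O'Brien-Fleming-type 2.93/2.07, interim lower limit 0: error about 5.2%, power about 87%. In points, the interim limits are about 18.7 and 0.
- Triangular 2.33/2.19, interim lower limit 0.78: error about 5.2%, power about 83%.

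Restate the power for the boundaries chosen. The cost is protocol wording, a check of one figure and a stated power below 90%; no extra patients are needed if the lower power is accepted. With the O'Brien-Fleming-type limits, early superiority stops at the design effect fall from 47% to 24%. With the triangular limits they stay at 47%.
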